### **12.4.3 Description of analysis sets**

There will be 2 analysis sets considered in this study: the safety analysis set and the PK analysis set. The safety analysis set will include all patients who have taken at least one dose of the trial medication. The PK analysis set will include all patients who completed both treatment periods of the PK Phase of the study and who have evaluable PK data. However, PK parameters will be calculated for all individuals where plasma concentration data is available.

Data from the patients who withdraw or are discontinued from the study, or who have missing values for other reasons, will be included in the analysis in such a way as to minimize any possible bias.

A strategy for dealing with PK data from the PK Phase of the study that is affected by protocol deviations will be agreed upon by the study team physician, pharmacokineticist, and statistician before any formal statistical analysis is performed.

### **12.4.4 Methods of statistical analysis**

#### **12.4.4.1 Pharmacokinetics**

For both the PK phase and the Continued Supply Expansion Phase, plasma concentration data and PK parameters will be listed and summarised descriptively by dose level and formulation administered using the appropriate standard summary statistics.

Within each cohort of the PK phase, the comparative bioavailability of the Melt-extrusion (tablet) formulation compared to the Gelucire® 44/14 (capsule) formulation will be estimated using an analysis of variance with factors for patient, formulation and period. The associated 90% confidence interval will also be calculated. Prior to analysis,  $C_{\max}$  and AUC values will be log-transformed.

All data will be listed and summarised as described in Section [12.6.1](#).

The plasma concentration-time data will be presented graphically via both individual and mean plots. Where plots are provided, an appropriate measure of variation may also be included.

#### **12.4.4.2 Archival tumour tissue samples (optional for Group 6, 7 and 8 patients only)**

Data arising from the exploratory biomarker analysis from Group 6, 7 and 8 patients will be detailed in a separate exploratory analysis SAP and reported outside of the main CSR.

#### **12.4.4.3 Nausea, vomiting and fatigue data (Group 8 patients only)**

Data arising from the characterisation of the common low grade AEs associated with AZD2281 (nausea, vomiting and fatigue) will be reported outside of the main CSR.

#### **12.4.5 Determination of sample size**

This study is an investigation of the comparative bioavailability of a new Melt-Extrusion (tablet) formulation of AZD2281 compared to the current Gelucire® 44/14 (capsule) formulation. There are no formal statistical analyses of the data planned and no formal sample size calculations have therefore been performed. The size of this study is based upon the desire to gain adequate PK information on the Melt-Extrusion (tablet) formulation whilst exposing as few patients as possible to study procedures.

Within the continued supply expansion phase, tablet doses (commencing at 250 mg bid) with potentially higher average exposure values than the 400 mg capsule dose will be explored and thus, in group 6 and 7 of the continued supply expansion, approximately 15 patients per arm (including at least 10 gBRCA ovarian cancer patients) are required to assess the safety and tolerability of these doses. In addition, as an exploratory measure of clinical activity, to rule out a significant difference between the melt-extrusion (tablet) formulation and the Gelucire® 44/14 (capsule) formulation, change in tumour size at eight weeks will be compared between the tablet dose arm(s) and the 400 mg bid capsule dose arm.

In Group 8, approximately 15 patients per treatment arm will be randomised. In a similar way as per the earlier expansion groups, change in tumour size will be evaluated.

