The objective of the continued supply expansion phase of the study as set out in the previous protocol amendment is to explore the safety and tolerability of AZD2281 following multiple dosing of a melt-extrusion tablet formulation. The 200 mg bid AZD2281 tablet dose was selected, based upon pharmacokinetic modelling of the single dose tablet exposure data obtained from the PK phase of the study, as a dose which would best match the range of steady state exposures ( $C_{ss \text{ max}}$  and  $AUC_{ss}$ ) previously observed following 400 mg bid AZD2281 capsule dosing.

Analysis of data from the on-going continuous supply expansion phase has shown that the 200 mg bid tablet dose does achieve exposures within the range of those seen following dosing at 400 mg bid AZD2281 with the capsule formulation. A direct intra-subject comparison of steady state exposure has shown that, although the gmean  $C_{ss \text{ max}}$  achieved following these doses of the two formulations was very similar, the gmean  $AUC_{ss}$  was approximately 20% lower following the tablet dose. The 200 mg bid tablet dose was very well tolerated but seemed to demonstrate lower anti-tumour activity compared to the 400 mg bid capsule dose.

As a result of these data, in order to identify a tablet dose which will be both tolerated by patients and provide comparable clinical activity to the 400 mg bid capsule dose, the safety and tolerability of higher doses of the tablet formulation, commencing at 250 mg bid, will be explored. This investigation of higher tablet doses will also support greater understanding of

the single and steady state pharmacokinetics of AZD2281 following dosing with the tablet formulation.

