#### **4.1.2.4 Randomised comparison between tablet and capsule**

Following the completion of the dose escalation tolerability assessment up to 400 mg bid AZD2281, approximately 45 patients will be randomised to Group 6 to assess the multiple dose safety profile of the Melt-extrusion (tablet) formulation in a comparative setting. The patients will be randomised on a 1:1:1 ratio to the following active treatment arms:

- Treatment A: A tablet dose between 250mg and the higher tablet dose taken into the expansion that has been shown to be safe and tolerable
- Treatment B: 400 mg bid dosing with AZD2281 Gelucire® 44/14 (capsule) formulation
- Treatment C: 400 mg bid AZD2281 tablet dose (or lower if 400 mg bid is not tolerated).

If dose escalation continues beyond 400 mg bid, following the completion of the dose escalation tolerability assessment up to a dose defined by the SRC, approximately 30 patients may be randomised to Group 7 to assess the multiple dose safety profile of the Melt-extrusion (tablet) formulation in a comparative setting. The patients will be randomised on a 1:1 ratio to the following active treatment arms:

- 
- Treatment A: The highest bid tablet dose deemed tolerable by the SRC following the dose escalation phase
  - Treatment B: 400 mg bid capsule

Randomisation will be stratified based on primary tumour type (breast cancer or ovarian cancer). There must be at least 10 gBRCA ovarian patients in each arm.

Regardless of the formulation the patient is treated with or the treatment group assigned to, all patients may receive continuous treatment with the assigned formulation for as long as they remain free from intolerable toxicity and, in the Investigator's opinion, are receiving some clinical benefit from AZD2281 and do not meet any other discontinuation criteria.

Patients who experience NCI-CTCAE of grade 3 or 4 toxicity and meet the criteria outlined in Section 5.5.1 for AZD2281 will have their study medication stopped. The safety follow-up should be continued as outlined in the study schedule.

Once patients receiving AZD2281 have been discontinued from study medication, other treatment options will be at the discretion of the Investigator.

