### **12.6.3 Efficacy data**

The efficacy data from Group 1, 6, 7 and 8 of the Continued Supply Expansion Phase will be summarised by dose, formulation (capsule or tablet) and schedule and is described below.

Summaries and waterfall plots of percentage change from baseline in sum of target lesions will be presented, and this data will also be analysed by analysis of covariance fitting baseline sum of target lesions as a continuous covariate and treatment group as a factor. Summary statistics will be presented for best overall response according to RECIST. PFS will be summarised using Kaplan-Meier estimates over time and will be displayed graphically.

Summaries of CA-125 response and the corresponding percentage change from baseline, will also be presented.

Summaries will be presented for the overall population and for the gBRCA ovarian cancer subgroup.

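### Section 12.4.5 presents the week-8 tumour-size comparison as ruling out a tablet–capsule difference, but without a margin and at about 15 patients per arm a non-significant ANCOVA would not rule out a material loss of activity

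*Protocol*

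**What the plan says.** Section 12.4.5 sets the size of Groups 6 and 7 on safety grounds: "approximately 15 patients per arm (including at least 10 gBRCA ovarian cancer patients) are required to assess the safety and tolerability of these doses". It then adds a second use for the same patients. It describes this use "as an exploratory measure of clinical activity, to rule out a significant difference between the melt-extrusion (tablet) formulation and the" capsule formulation, and specifies that "change in tumour size at eight weeks will be compared between the tablet dose arm(s) and the 400 mg bid capsule dose arm". The section gives no margin, SD, confidence level or power for this comparison, and opens by stating that "There are no formal statistical analyses of the data planned and no formal sample size calculations have therefore been performed".

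The method is in section 12.6.3, and in the same terms in section 12.4.2.7: percentage change in the sum of target lesions is "analysed by analysis of covariance fitting baseline sum of target lesions as a continuous covariate and treatment group as a factor". Section 12.6.3 adds: "Summaries will be presented for the overall population and for the gBRCA ovarian cancer subgroup". Group 6 allocation is described in section 4.1.2.4: "The patients will be randomised on a 1:1:1 ratio to the following active treatment arms"; Group 7 is 1:1 against the capsule.

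Section 2.3 explains why higher tablet doses are studied. The 200 mg bid tablet gave roughly 20% lower steady-state AUC and appeared less active than the capsule, and the aim is a tablet dose that is tolerated and will "provide comparable clinical activity to the 400 mg bid capsule dose".

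**The concern.** To rule out a difference, one needs a stated size of difference and a confidence interval that excludes it. Section 12.4.5 supplies only the verb. With an ANCOVA and no margin, a reader can take a non-significant treatment term as meeting the stated purpose. Non-significance does not establish similarity at any sample size, and with arms this small it is a common result even when the true difference is large.

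The question matters to this phase because the programme moved to higher tablet doses partly on a suspicion of lower anti-tumour activity. If a non-significant week-8 result were reported as having ruled out a difference, the tablet could appear to match the capsule on data compatible with a clinically important deficit. The guaranteed ovarian subgroup, at 10 per arm, is more exposed still.

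**Working it through.** **The plan's own figure.** The 15 per arm cannot be reproduced from a calculation, because the protocol says none was done. The totals agree: 3 × 15 = 45 for Group 6 and 2 × 15 = 30 for Group 7. The useful check is what 15 and 10 per arm can exclude.

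**Inputs**
- n = 15 per arm, and n = 10 per arm for the guaranteed ovarian minimum (section 12.4.5).
- Two-arm ANCOVA with one covariate (section 12.6.3), so df = 2n − 3.
- 95% interval and two-sided 5% test: assumed, since the protocol gives no level.
- Residual SD of week-8 percentage change after baseline adjustment: not in the documents. Assumed 20, 30 and 40 percentage points.
- All patients assumed to contribute a week-8 value; any loss widens the intervals.

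**Step 1: interval half-width.** Half-width = t(0.975, 2n − 3) × SD × √(2/n).
- n = 15: 2.052 × 0.3651 = 0.749 SD.
- n = 10: 2.110 × 0.4472 = 0.944 SD.

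| Assumed SD (points) | 15 per arm | 10 per arm |
|---|---|---|
| 20 | 15.0 | 18.9 |
| 30 | 22.5 | 28.3 |
| 40 | 30.0 | 37.7 |

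Even an observed difference of exactly zero would leave deficits of this size inside the interval. For scale, Appendix F defines a partial response as a decrease of at least 30% in the sum of longest diameters. Fitting all three Group 6 arms in one model (df = 3n − 4 = 41 at n = 15) changes 0.749 SD only to 0.737 SD.

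**Step 2: how often a real loss would be non-significant.** Take a true 20-point loss, d = 20/SD, with noncentrality d × √(n/2) and the noncentral t distribution on 2n − 3 df.

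| Assumed SD | d | Non-significant, 15 per arm | Non-significant, 10 per arm |
|---|---|---|---|
| 20 | 1.00 | 25% | 44% |
| 30 | 0.67 | 58% | 71% |
| 40 | 0.50 | 74% | 82% |

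**Step 3: what ruling out would require.** Normal approximation, one-sided 2.5%, 80% power, true difference zero: n per arm = 2 × ((1.960 + 0.842)/m)², with margin m in SD units.
- m = 0.5 SD: 2 × (2.802/0.5)² = 62.8, so 63 per arm.
- m = 0.75 SD: 27.9, so 28 per arm.
- m = 1.0 SD: 15.7, so 16 per arm.

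About 15 per arm is therefore close to enough to exclude a difference of a full SD (power about 78%), and well short for anything materially smaller.

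**The case against.** The strongest reply is that this is an explicitly exploratory comparison in a phase I study. The primary objective of Groups 6 and 7 is safety and tolerability, the efficacy objective is to describe the data, and the arms were sized on safety. All of that stands, so the absence of a power calculation is not a fault. An ANCOVA also yields an estimate and interval as readily as a p-value, the protocol states no success criterion for it, and details of presentation may properly sit in the SAP. What remains is the inferential purpose written into section 12.4.5, which an SAP would inherit.

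Three stronger readings are tempting and should be resisted.
- A reader might infer that 15 per arm can rule out nothing. That depends on a margin and SD the protocol does not give; step 3 shows that a difference of about 1 SD could be excluded with reasonable power. It is also arguable that *significant* was meant loosely as *large*, though the text does not say so.
- A reader might infer that a missed difference is always the likelier outcome. For a 20-point loss that is not so when the SD is 20: the miss rate is 25% at 15 per arm and 44% at 10.
- A reader might infer that the trial will act on a non-significant result. No section ties a decision to one. The synopsis bases the final dose on tolerability and acceptability, the Safety Review Committee reviews safety and PK data (section 4.1.4), and the arm-switching clause in section 6.2.3.2 is triggered by a demonstrated difference, not by its absence.

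The opening sentence of section 12.4.5 about no formal analyses might also be read as contradicting the ANCOVA. It stands in the paragraph on comparative bioavailability and can mean that no hypothesis tests are planned. The present point does not rest on it.

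**Conclusion.** The point holds as one of inferential wording. Section 12.4.5 claims for the week-8 comparison a property that the design does not have: with no margin, a non-significant ANCOVA would not rule out a material loss of tablet activity, and it could be misread as support for the comparable-activity aim in section 2.3. In SD units the 95% half-width is about 0.75 at 15 per arm and 0.94 at 10, on the assumption of complete week-8 data; these do not depend on an assumed SD. The percentage-point widths and miss rates do depend on the assumed SDs of 20 to 40 points. The matter is moderate: it concerns a secondary, exploratory comparison and leaves the safety objectives and sample size untouched, but it changes what may legitimately be concluded about efficacy.

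**What to change.** In section 12.4.5, replace the phrase about ruling out a significant difference with wording such as: *the difference in mean percentage change in tumour size at week 8 (tablet minus capsule) will be estimated from the ANCOVA with its 95% CI; non-significance will not be interpreted as evidence of similar activity.* Add the expected half-width in SD units, about 0.75 SD for 15 per arm and 0.94 SD for 10 per arm, which needs no outside SD. Leave the sentence about no formal analyses alone, since deleting it would strip the following clause on sample size of its reason.

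No extra patients, visits or assessments are needed. The only downside is that the stated claim becomes weaker. If the sponsor does want to exclude a difference, a margin and a matching sample size would have to be stated; on the assumptions in step 3, a 0.5 SD margin needs 63 per arm.

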#### **12.5 Interim analysis**

During the PK phase of the study an interim analysis will be performed on recorded safety and PK data retrieved from Cohorts 1 and 2 before proceeding to Cohort 3 randomisation. The objective of such an analysis is to better define the higher dose level for the Melt-extrusion (tablet) formulation in Cohort 3.

During the Continued Supply Expansion Phase, an interim analysis of safety data will be performed following the completion of 3 cycles of treatment with the tablet formulation for all patients. The objective of such an analysis is to get an early indication of the emerging safety profile of the tablet formulation. In addition, the steady state plasma concentration data obtained from Group 2 will be analysed once all PK sampling in this group has completed to provide reassurance that the tablet dose being used for continuous dosing is providing the equivalent steady state exposure as the capsule formulation.

Data from the Continued Supply Expansion Phase will be evaluated on an on-going basis to monitor emerging safety and efficacy profile of the tablet formulation.

## 12.6 Data presentation

### 12.6.1 Pharmacokinetics

The AZD2281 plasma concentration data and PK parameters will be listed individually for each patient and summarised according to the dose and formulation (capsule or tablet) received. Summaries will be constructed appropriately for the cohorts of the PK Phase and Continued Supply Expansion Phase.

Summaries of AZD2281 plasma concentration at each time point will present:

- The geometric mean (gmean, calculated as  $\exp[\mu]$ , where  $\mu$  is the mean of the data on a log scale);
- Coefficient of variation (CV, calculated as  $100 \times \sqrt{[\exp(s^2)-1]}$ , where  $s$  is the standard deviation of the data on a log scale);
- Gmean  $\pm$  standard deviation (SD) (calculated as  $\exp[\mu \pm s]$ );
- Arithmetic mean calculated using untransformed data;
- SD calculated using untransformed data;
- Minimum;
- Maximum;
- Number of observations.

Summaries of AZD2281 AUC, AUC0-t, Cmax, Css,max, Css,min and AUCss will present:

- The gmean (calculated as  $\exp[\mu]$ , where  $\mu$  is the mean of the data on a log scale);
- Coefficient of variation (CV, calculated as  $100 \times \sqrt{[\exp(s^2)-1]}$ , where  $s$  is the standard deviation of the data on a log scale);
- Arithmetic mean calculated using untransformed data;
- SD calculated using untransformed data;
- Minimum;
- Maximum;
- Number of observations.

Summaries of AZD2281 CL/F, t1/2 and Vz/F should present:

- 
- Arithmetic mean;
  - SD;
  - Minimum;
  - Maximum;
  - Number of observations.

Summaries of AZD2281tmax will present:

- Median;
- Minimum;
- Maximum;
- Number of observations.

Non-quantifiable (NQ) values of plasma concentrations will be handled as follows:

[figure not shown]
- If, at a given time point 50 % or less of the plasma concentrations are NQ, the gmean, CV, gmean ± SD, arithmetic mean and SD will be calculated by substituting the limit of quantification (LOQ) for values which are NQ;
- If more than 50 %, but not all, of the concentrations are NQ, the gmean, CV, gmean ± SD, arithmetic mean and SD will be reported as not calculable (NC);
- If all the concentrations are NQ, the gmean and arithmetic mean will be reported as NQ and the CV, gmean ± SD and SD as NC.

If the calculation of the gmean – SD results in a value less than the LOQ, NQ will be displayed.

### **12.6.2 Safety data**

All AEs will be listed for each patient and summarised for each treatment by body system and preferred term assigned to the event using Medical Dictionary for Regulatory Activities (MedDRA) vocabulary. AEs will also be assigned a maximum NCI-CTCAE grade by the Investigator and summaries will be performed by maximum NCI-CTCAE grade using NCI CTCAE Version 3.

All laboratory safety data, incorporating haematology, clinical chemistry and urinalysis data will be listed for each patient. Haematology and clinical chemistry values outside the standard reference ranges will be highlighted. Numerical laboratory data will be summarised by the dose and formulation (capsule or tablet) received. Summaries will be constructed

appropriately for the cohorts of the PK Phase and Continued Supply Expansion Phase. Standard summary statistics (mean, standard deviation, minimum, median, maximum, and number of subjects) will be produced. NCI-CTCAE shift tables of laboratory parameters will be produced.

Pulse and BP will be listed by patient and summarised by the dose and formulation (capsule or tablet) received. Summaries will be constructed appropriately for the cohorts of the PK Phase and Continued Supply Expansion Phase. Standard summary statistics for the absolute value at each protocol time and the change from screening baseline to all subsequent protocol assessments will be produced.

ECG and physical examination details will be listed individually by patient.

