## Continued Supply Expansion Phase (including dose escalation groups)

- **Primary outcome variable**

- Safety (all patients): AEs, physical examination, vital signs including BP, pulse and body temperature ECG and laboratory findings including clinical chemistry, haematology and urinalysis.

- **Secondary outcome variables**

- The following single dose PK parameters will be derived for the Melt Extrusion (tablet) formulation and the Gelucire® 44/14 (capsule) formulation:  $C_{max}$ ,  $C_{min}$  and  $AUC_{0-8}$  (Group 8 tds schedule),  $AUC_{0-12}$  (all patients on bd schedule) and  $AUC_{0-24}$  (Group 8 od schedule).
- The following multiple dose PK parameters will be derived for the Melt Extrusion (tablet) formulation and the Gelucire® 44/14 (capsule) formulation:  $C_{ss,max}$ ,  $C_{ss,min}$  and  $AUC_{ss}$
- Efficacy: change from baseline in the sum of target lesions (as per RECIST), Progression-Free Survival (PFS), best overall response, CA-125 response
- Preliminary assessment of the effect of food on the exposure of AZD2281 tablet (Group 8 patients only) – Day 8 : Day 1  $C_{max}$  and  $AUC_{0-24}$  ratios

- **Exploratory outcome variables**

- Exploratory biomarker analysis of the activity of AZD2281 and correlation with disease progression/response to therapy will be conducted. If available, archival tumour samples from patients enrolled Group 6, 7 and 8 will be collected in order to achieve this objective.

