### **Treatment Periods**

On the first day of each treatment period, safety assessments will be performed prior to dosing (laboratory tests [haematology, clinical chemistry and urinalysis], vital signs and body weight [body weight only at Treatment Period 1, Day 1], ECG, physical examination, AEs and concomitant medications) and ECOG performance status recorded. Patients will be given a single dose of either AZD2281 formulation (Sequence 1 or Sequence 2) on the morning of Treatment Period 1 (Day 1) and Treatment Period 2 (Day 8). Blood samples for the determination of plasma concentrations of AZD2281 will be collected pre-dose and at 0.5, 1.0, 1.5, 2, 3, 4, 6, 8 & 10 hours for both treatment periods. Patients may remain in hospital on the first day of Treatment Periods 1 and 2. In addition, patients who live a distance from the hospital may also stay in the hospital or nearby the hospital for Treatment Period 1, Day 2 and Treatment Period 2, Day 9.

On Treatment Period 1 (Day 2) and Treatment Period 2 (Day 9), safety assessments will be performed - vital signs, AEs and concomitant medications. A blood sample for AZD2281 analysis will be taken 24 hours post-dose.

On Treatment Period 1 (Day 3) and Treatment Period 2 (Day 10), safety assessments will be performed - vital signs, AEs and concomitant medications. A blood sample for AZD2281 analysis will be taken 48 hours post-dose.

Treatment periods will be separated by a washout period of 6–14 days from the first AZD2281 dose.

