**Table 5 Study schedule for PK Phase**

Visit	PK Phase									Continued Supply Phase			Treatment Discontinuation
	Screening		Treatment Period 1			Treatment Period 2			Post PK Phase Follow-up a 7 days since last dose	Continuous treatment b 7 days after end of PK Phase	Final Follow-up k 30 days since last dose		
Day	-28 to -1	-7 to -1	1	2	3	8	9	10					
Adverse Events l	X	X	X	X	X	X	X	X	X		X	X	X
Concomitant medications	X	X	X	X	X	X	X	X	X		X	X	X
AZD2281 dispensed/returned			X			X			X		X		

a Following the last dose of AZD2281 in the PK Phase, patients should have a post-study visit within 7 days.

[figure not shown]
b The Continued Supply Phase is scheduled 7 days after the end of the PK Phase. Patients may then continue to receive treatment with the Gelucire® 44/14 (capsule) formulation (at 400 mg orally bid [ie, 8 capsules bid]). Patients that wish to continue onto the Continued Supply Phase of the study will have safety assessment performed approximately every 28 days (28 days = 1 cycle). There will be the exception of patients being seen less after the first three monthly reviews - if the Investigator considers the patient to be tolerating AZD2281 well, in which case patients should be assessed by the Investigator at least quarterly with interim telephone contact and monthly laboratory assessments (undertaken by local hospital / General Practitioner). Once the PK team at AstraZeneca have confirmed the exposure ratio between the Gelucire® 44/14 (capsule) and Melt-Extrusion (tablet) formulations, patients may be given the option to switch from the Gelucire® 44/14 (capsule) formulation (400 mg orally bid) to receive the equivalent Melt-Extrusion (tablet) formulation of AZD2281.

c Height at screening only. Physical examination to be performed throughout the study.

d If assessed within 7 days before enrolment and meets the stated eligibility criteria (if applicable), it need not be repeated on Day 1 of cycle 1 unless Investigator believes that it is likely to have changed significantly.

e Vital signs include BP, pulse and body temperature. Patient is to be in the supine position for BP and pulse. Body weight will be measured at screening, Treatment Period 1, Day 1 and on the Final Follow-up Visit.

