### **7.2 Screening and demography procedures**

#### **7.2.1 Screening**

The following assessments and procedures should be performed within 28 days prior to first dose of study treatment. For details of the schedule and nature of the assessments, see below.

- Study eligibility (Inclusion/Exclusion criteria) (within 28 days and 7 days prior to study treatment start);
- Signed informed consent (within 28 days prior to study treatment start);
- Demographics (date of birth, gender, and race) (within 28 days prior to study treatment start);
- Serum or urine pregnancy test for women of childbearing potential (within 28 days prior to study treatment start);

- Medical and surgical history (within 28 days prior to study treatment start), including previous cancer and radiotherapy and history of blood transfusions in the previous 6 months;
- Current and concomitant medications including previous cancer therapies (if applicable) (within 28 days and 7 days prior to study treatment start);
- Physical examination, ECOG performance status, vital signs (BP, pulse and body temperature), body weight and height (within 28 days prior to study treatment start);
- ECG (within 7 days prior to study treatment start);
- Haematology, clinical chemistry and urinalysis (within 28 days prior to study treatment start);
- AE recording (within 28 days and 7 days prior to study treatment start);

The following assessments will only be performed for those patients who will be participating in Group 1, 6, 7 and 8 of the Continued supply phase expansion:

- Tumour assessment (CT or MRI scans of chest, abdomen and pelvis for breast cancer and abdomen and pelvis for ovarian cancer with other regions as clinically indicated for the assessment of disease). An historical scan meeting the RECIST criteria as defined in [Appendix F](#) can be used for baseline assessment, but this must be performed no more than 28 days before the first dose of study medication.
- CA-125 (within 28 days prior to study treatment start) in ovarian cancer patients only

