#### **7.3.5.1 Pulse and blood pressure**

At each study visit, supine BP and pulse will be measured using a semi-automatic BP recording device with an appropriate cuff size. The date and time of collection and measurement will be recorded on the appropriate CRF.

Measurements will be made after the patient has been resting supine for a minimum of 5 minutes. Two readings should be taken and the average recorded.

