#### **12.4.2.5 Pulse and blood pressure**

Absolute pulse and BP data will be listed and summarised using standard summary statistics by treatment.

[figure not shown]

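### Section 12.6.2 takes pulse and blood pressure change from screening, not from the last value before first dose, so within-arm change summaries include drift that precedes treatment (minor)

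*Protocol*

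**What the plan says.** **Analysis.** Protocol 12.6.2 (Safety data) has pulse and blood pressure listed by patient and summarised by dose and formulation. It asks for absolute values at each protocol time, and adds that "the change from screening baseline to all subsequent protocol assessments will be produced". Section 12.4.2.5 mentions only absolute values: "Absolute pulse and BP data will be listed and summarised using standard summary statistics by treatment". No other section gives a baseline for pulse or blood pressure.

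**Collection.** The screening list in 7.2.1 includes "Physical examination, ECOG performance status, vital signs (BP, pulse and body temperature), body weight and height (within 28 days prior to study treatment start"). Section 7.3.5.1 then states: "At each study visit, supine BP and pulse will be measured using a semi-automatic BP recording device with an appropriate cuff size". It also has the date and time of measurement recorded on the case report form. For the PK Phase, section 4.1.1 (Treatment Periods) says: "On the first day of each treatment period, safety assessments will be performed prior to dosing"; vital signs are among those assessments. Tables 6 and 7 schedule vital signs on Day 1 for Groups 1 to 8.

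**Waiver.** A footnote to Table 5, repeated in Tables 6 and 7, says: "If assessed within 7 days before enrolment and meets the stated eligibility criteria (if applicable), it need not be repeated on Day 1". The waiver falls away if the investigator thinks the finding has probably changed materially.

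**Role.** The synopsis names "vital signs including BP, pulse and body temperature" within the primary safety variable of the expansion phase. Vital signs are also a secondary variable in the PK Phase.

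**The concern.** A table of change from baseline is normally read as change since treatment began. Here the reference is a visit that can precede the first dose by four weeks, in patients with advanced cancer whose condition may move in that time. That movement cannot be an effect of the drug, yet the table counts it as change. A reading taken on Day 1 before any dose would also appear in the table as a post-baseline value.

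The exposure is greatest in the dose escalation groups (Group 3 onwards). Each recruits a minimum of 6 patients at one dose, with no concurrent arm against which the drift could be set.

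The protocol takes more care elsewhere. CA-125 response is measured from the last pre-treatment sample (12.3.4). Baseline scans should ideally be as near to the start of treatment as possible (Appendix F, 4.1). The ECG baseline is taken afresh on entry to the Continued Supply Phase (7.3.5.2).

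**Working it through.** The plan states no figure that depends on this baseline, so there is nothing to reproduce. The check is one of timing and of algebra.

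**1. Age of the reference value**
- Oldest screening reading at first dose: 28 days (7.2.1; Tables 5 to 7 show Day -28 to -1).
- With the last pre-dose value as baseline: the same day where Day 1 is measured. Where Day 1 is waived, the reading is at most 7 days old at enrolment. The waiver is counted from enrolment and not from first dose, so its age at dosing may be slightly more.
- A screening reading older than the waiver limit therefore triggers a Day 1 reading. Where the screening value is most out of date, a fresher one is scheduled.

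**2. What the change contains**

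Let S be the screening value, P the last pre-dose value and Y an on-treatment value. Then

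Y − S = (Y − P) + (P − S).

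The last term is fixed before the first dose. With P as baseline it drops out. For a waived patient P is the screening reading itself, so the term is already zero and the fix changes nothing.

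**3. Effect in a small single-arm group**

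For n patients, the mean change from screening equals the mean of (Y − P) plus the mean of (P − S). With n = 6, a drift of d mmHg in one patient moves the group mean by d/6, and a drift common to all six moves it by the whole of d.

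**4. Can a reader undo it from the planned tables?**
- The mean, approximately: absolute values at Day 1 are summarised too. The subtraction is exact only if the same patients contribute at both times, which waivers and later dropout prevent.
- The standard deviation, minimum and maximum of change: no. These depend on within-patient differences and cannot be recovered from summaries of absolute values. They can be recomputed only from the listings.

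**5. The crossover contrast**

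With one shared screening value, (tablet − S) − (capsule − S) = tablet − capsule. The screening value cancels within each patient.

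**6. Randomised parallel arms (Groups 1, 6, 7 and 8)**

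The drift term arises before treatment, so randomisation makes its expected value the same in each arm. The difference between arms in mean change is not biased by it.

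**The case against.** **Low stakes.** No formal comparison of safety data is planned for any group, the dose-limiting toxicity criteria in 6.2.4.3 name no pulse or blood pressure change, and the clinical experience in 2.1.5 lists no such effect. Absolute values are also reported at each time, so a mean shift before dosing would be visible. All of this stands, and it is why the point is minor.

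**Screening is the one uniform reference.** Every patient must have it, whereas Day 1 can be waived, and 28 days is the outer edge of the window and not the typical gap. This is fair, but a rule of last value before first dose also gives every patient a baseline.

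**The SAP can settle it.** Section 12.4.1 leaves details of summaries to the SAP, which is not shown. However, 12.6.2 names the reference visit, so a SAP that used another would depart from the protocol.

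**Two stronger readings that the documents do not support.**

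A reader might infer that the tablet-capsule comparison in the PK Phase is distorted. The two doses are "separated by a washout period of 6–14 days from the first AZD2281 dose", so screening can be up to 28 + 14 = 42 days before the second dose. But the shared value cancels, as shown in the working, and 1:1 randomisation to sequence balances a period shift. Only change within a period is affected.

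A reader might then want each period's own pre-dose value as baseline. That is a trade-off. Let rb be the correlation between readings in different periods (all such pairs taken as equal) and rw the correlation between readings in the same period. The variance of the tablet-capsule difference is 2(1 − rb)SD² with the shared baseline and 4(1 − rw)SD² with period baselines. For illustrative correlations, none of them from the protocol:

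| rb | rw | shared | period-specific |
|---|---|---|---|
| 0.5 | 0.7 | 1.0 SD² | 1.2 SD² |
| 0.6 | 0.7 | 0.8 SD² | 1.2 SD² |
| 0.5 | 0.8 | 1.0 SD² | 0.8 SD² |

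The period-specific baseline is noisier in two of the three cases, so it is not a required change.

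**Conclusion.** The point holds as a minor flaw in a descriptive summary. Section 12.6.2 fixes a reference that can be 28 days old at first dose, although a later pre-dose reading is scheduled whenever vital signs were not assessed within 7 days before enrolment. Within-arm summaries of pulse and blood pressure change therefore mix pre-treatment drift with on-treatment change, and a Day 1 pre-dose reading is counted as post-baseline.

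The size in mmHg, and any gain in precision, cannot be stated: the protocol gives neither a standard deviation nor a correlation for these measurements. The conclusion does not extend to the crossover contrast or to bias between randomised arms, and no dosing decision is tied to this table.

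It rests on one assumption. For Groups 1 to 8 the schedule shows a Day 1 reading but does not itself say that it precedes the dose. The waiver suggests that it does, and the recorded time of measurement allows a check.

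**What to change.** In 12.6.2, replace the reference to a screening baseline with a definition: baseline is the last pulse or blood pressure value before the first dose of AZD2281, that is, the Day 1 pre-dose value, or the screening value where the Day 1 repeat was waived. Changes are then tabulated only for assessments after first dose, with the absolute-value summaries left as they are. Section 12.4.2.5 is silent on baseline and needs no change.

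The cost is one sentence and one programming rule, using data and measurement times already collected. No visit or procedure is added.
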